10 STATISTICAL CONSIDERATIONS

10.1 STATISTICAL HYPOTHESES

Primary Efficacy Endpoint(s):

Assess the feasibility of a short course of immune modulating therapy with daily mycophenolate mofetil (MMF). We will start to test the hypothesis that MMF for 12 weeks will safely attenuate immunogenicity conferred by pegloticase as determined by the proportion of participants achieving and maintaining a serum urate ≤ to 6 mg/dL through 12 weeks, compared to concurrent controls. After 12 weeks of co-administration, all participants will continue on pegloticase for an additional 12 weeks without combination MMF therapy to evaluate the durability and safety of this approach

Primary Safety Endpoint(s):

Assess the incidence and types of adverse events /infusion reactions.

Secondary Endpoints:

1) Determine the 6 month durability of immune modulation after discontinuation of the short course of MMF by: a) assessing the absolute change in serum urate from baseline to Week 24, and Week 12 to Week 24, and b) determining the proportion of participants with serum urate ≤ 6 mg/dL through 24 weeks, and Week 12 to Week 24; 2) Identify and characterize the pegloticase immune response by immunoglobulin isotypes (IgG and IgM), specificities, and antibody titer, and 3) Examine patient reported outcomes (PROs) using the National institute of Health (NIH) supported Patient Reported Outcomes Measurement Information System (PROMIS) and Gout Impact Scale (GIS) instruments.

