10.4.3 ANALYSIS OF THE PRIMARY SAFETY AND SECONDARY ENDPOINT(S)

The *primary safety aim* will examine the number of patients experiencing the event and the total number of events, their severity and relatedness to study drug will be summarized and all AEs and SAEs reported. Ascertaining safety outcomes will be mostly descriptive and the confidence intervals will remain wide for the proportion of responders, based on n = 32, but strong evidence to proceed with a larger trial is necessary.

The *secondary aims* are to: 1) Determine the 6 month durability of immune modulation after discontinuation of the short course of MMF by: a) assessing the absolute change in serum urate from baseline to Week 24, and Week 12 to Week 24, and b) determining the proportion of participants with serum urate ≤ 6 mg/dL through 24 weeks, and Week 12 to Week 24; 2) Identify and characterize the pegloticase immune response by immunoglobulin isotypes (IgG and IgM), specificities, and antibody titer, and 3) Examine patient reported outcomes (PROs) using the NIH supported Patient Reported Outcomes Measurement Information System (PROMIS)^{57,58} and Gout Impact Scale (GIS)^{59,60} instruments. For safety we will assess the incidence and types of adverse events / infusion reactions. The number of patients experiencing the event and the total number of events, their severity and relatedness to study drug will be summarized and all AEs and SAEs reported. Secondary endpoints including AEs across groups will be summarized using frequency and percentages. Continuous secondary outcome variables will be summarized using means with standard deviation (SD), and/or median and interquartile ranges (IQR) with 95% confidence intervals and compared by groups using t-tests or Wilcoxon tests as appropriate. Pegloticase Ab titers will be qualitatively analyzed for possible relationships with sUA lowering and the risk of IRs. Six month durability of response to MMF will be explored to assess if there is a threshold

^{*} Dash indicates a highly significant 2 tailed p-value using Fishers exact test

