effect or pattern of response with anti-pegloticase Ab titers/types. This aim will be supported by analyses that compares the treatment groups using two group t-tests and regression analyses that include the time of the sampling (an offset) to adjust for any 12 or 24 week samples that may be taken earlier at the time of failure or dropout. Repeated measures assessments using all Ab data (both data points: baseline and last observation) will be assessed using random effects in PROC MIXED to assess the variability in response over time. Comparisons will be assessed using pre-specified contrasts. Analyses of the sUA will be similarly assessed using PROC MIXED with random effects for participant. In addition, addressing the secondary aim: b) determining the proportion of participants with sUA ≤ 6 mg/dL through 24 weeks, and Week 12 to Week 24; will be examined using Fisher's exact test. Continuous models estimating the areas under the dose-time curve with estimation based on using the trapezoidal rule will be constructed and adjusted for time under study yielding an average sUA during the observation period. These areas under the curve will be compared using similar linear models with an offset for the time under study. Exploratory analyses will assess association of covariates within group areas under the curve; 2) Identify and characterize the pegloticase immune response by immunoglobulin isotypes (IgG and IgM), specificities, and Ab titer.

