These secondary outcome variables will be summarized using means with standard deviation, confidence intervals, and/or median and interquartile ranges, dependent on their distribution and plots of their response alone and in combination. Secondary endpoints will examine different definitions of sUA levels by plotting the initial values versus change values on the unbiased outcome results and time weighted averages; and 3) Examine PROs using the NIH supported Patient Reported Outcomes Measurement Information System (PROMIS)^{57,58} and Gout Impact Scale (GIS)^{59,60} instruments; these will use similar approaches of descriptive statistics, plots of PROs versus outcomes and correlations. The PROs will be summarized by change over time using means, 95% confidence intervals and compared between responder and non-responder status. We do not plan to control for the repeated testing using adjustments for multiple comparisons since this is a feasibility trial and since statistical significance is not the goal as it would be in a pivotal trial. The sample size is small and we see these secondary as well as primary analyses as descriptive. The p-values will be calculated, but will take the totality of the evidence into account in the interpretation. We considered using hierarchical testing such that each test would be done at the 0.05 level, but the low power argues that such could easily lead back to not considering secondary endpoints.

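### The arm comparison of serum urate change from baseline to Week 24 takes no account of baseline; adjusting for a pre-randomisation value costs almost nothing and may add precision

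*Combined protocol and SAP*

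**What the plan says.** Section 10.1 defines the durability endpoint as "assessing the absolute change in serum urate from baseline to Week 24, and Week 12 to Week 24". Section 10.4.3 gives the general rule for continuous secondary outcomes: they are "compared by groups using t-tests or Wilcoxon tests as appropriate".

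Section 10.4.3 then adds models:

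- **Antibody, regression.** The plan "compares the treatment groups using two group t-tests and regression analyses"; the regression carries an offset for sampling time.
- **Antibody, repeated measures.** "Repeated measures assessments using all Ab data (both data points: baseline and last observation) will be assessed using random effects in PROC MIXED". Contrasts are described as pre-specified but are not listed.
- **Urate, repeated measures.** "Analyses of the sUA will be similarly assessed using PROC MIXED with random effects for participant". No fixed effects are given.
- **Urate, area under the curve.** "These areas under the curve will be compared using similar linear models with an offset for the time under study".
- **Patient-reported outcomes.** Change over time is "compared between responder and non-responder status".

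No between-arm analysis names a baseline covariate, and the plan does not say which of the listed urate analyses is the main one. Section 10.4.3 describes the secondary and primary analyses as descriptive.

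The Schedule of Activities (Section 2.3) and the visit lists in Section 9 place urate draws at Visits 1 and 2. Randomisation and first dispensing are at Visit 2. Antibody samples are taken at Visits 1 and 3. The visit labelled baseline is Visit 3, after two weeks of randomised mycophenolate or placebo.

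**The concern.** A raw change score subtracts the whole of the baseline value, however weakly it predicts the later one. When the correlation is low and the two SDs are similar, the subtraction adds noise. With only 8 controls, a chance baseline difference between arms also passes in full into the estimated difference in change.

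The mixed models do not clearly avoid this. Consider two time points, complete data and baseline means left free to differ by arm. The group-by-time contrast is then the difference in mean change, with the precision of a change score. The antibody model has this two-point structure. For urate the plan does not say whether baseline is part of the outcome vector, a covariate or absent.

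At stake is the width of the interval for the between-arm urate comparison in a trial of 32, and how firmly it can inform a larger study.

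**Working it through.** **Inputs from the documents.** Allocation is 24 versus 8 (Sections 5.1 and 7.3). An effect of 1 SD is the size used for antibody titre in Section 10.4.1. Two-sided 0.05 is the level used for the full-scale trial in Section 10.2.

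**Assumed, because the documents give no value.** ρ is the correlation between baseline and Week 24, taken from 0 to 0.6. k is the baseline SD divided by the Week 24 SD, taken as 1 or 0.5.

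**The plan's own figure.** Section 10.4.1 gives 73% power for a 1 SD difference in titre and states no significance level for it. The standard error (SE) factor is √(1/24 + 1/8) = 0.408, so the noncentrality is 1/0.408 = 2.45 on 30 degrees of freedom. A pooled t-test gives 65.9% at two-sided 0.05 and 77.3% at 0.10. Simulated at 0.10, the Wilcoxon test gives 74.3% and the Welch test 74.5%. The stated figure is therefore approached at the pilot's 0.10 level with either of those tests.

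**Chance imbalance.** The SE of the baseline mean difference is 0.408 SD. The probability of an imbalance above 0.5 SD in either direction is 2 × [1 − Φ(0.5/0.408)] = 2 × [1 − Φ(1.22)], about 22%.

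**Variance per participant, in units of the Week 24 variance.**

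- Change score: Vc = 1 + k² − 2ρk, 30 degrees of freedom.
- Baseline-adjusted (ANCOVA, common slope): Va = (1 − ρ²) × [1 + 1/(32 − 4)] = (1 − ρ²) × 1.036, 29 degrees of freedom.
- Week 24 level alone: V = 1, 30 degrees of freedom.

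Power comes from the noncentral t distribution with noncentrality 1/(0.408 × √V). Example with ρ = 0.2 and k = 1: Vc = 1 + 1 − 0.4 = 1.60 and Va = 0.96 × 1.036 = 0.994. The SE ratio is √(0.994/1.60) = 0.79, and the noncentralities are 1.94 and 2.46.

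| ρ | Change, k = 1 | Change, k = 0.5 | Level alone | Adjusted | SE ratio, adjusted/change, k = 1 | SE ratio, k = 0.5 |
|---|---|---|---|---|---|---|
| 0 | 39% | 56% | 66% | 64% | 0.72 | 0.91 |
| 0.2 | 47% | 64% | 66% | 66% | 0.79 | 0.97 |
| 0.4 | 58% | 73% | 66% | 72% | 0.85 | 1.01 |
| 0.6 | 75% | 84% | 66% | 83% | 0.91 | 1.01 |

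A simulation of 20,000 trials per cell agreed within 1 point.

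With equal SDs, adjustment gains between about 7 and 25 points over the change score. With k = 0.5 it gains 8 points at ρ = 0 and 2 at ρ = 0.2; from ρ = 0.4 it gains nothing and gives up about 1. Against the level alone, nothing is gained at ρ of 0.2 or less.

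**A responder/non-responder pattern.** Week 24 urate may depend mainly on whether pegloticase still works. Simulating the response rates of 80% and 60% from Section 10.2, with non-responders returning to their baseline urate and an assumed baseline SD of 1 to 2 mg/dL, gives k of 0.25 to 0.49. Across that range the SE of the arm difference was 1.66, 1.71 and 1.78 for change, against 1.67, 1.68 and 1.72 adjusted. That is between a loss of 0.4% and a gain of 3.4%.

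**The case against.** **The gain may be close to nil.** A reader might infer from the equal-SD rows that the trial moves from about 39% to 64% power. The documents do not support that. They give no SDs and no correlation, and the pattern most likely to produce a low correlation also makes Week 24 urate much more variable than baseline. This objection stands, and it limits the size of the claim.

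**Adjustment is not always at least as precise.** A reader might take it as a general result that baseline adjustment cannot lose. With 3:1 allocation and slopes that differ by arm, a common-slope model can lose. In a deliberately extreme case (slopes 0 and 1, residual SD 0.6) the simulated SE was 0.371 adjusted against 0.314 for change.

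**Urate and titre are not left to t-tests alone.** Section 10.4.3 adds mixed models for both, and the antibody model contains baseline. What remains is that the fixed effects and the handling of baseline are unstated.

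**The antibody part of the decision to proceed is barely touched.** Section 10.4.1 plans a difference in titre level, not change, and Section 6.2 excludes prior pegloticase, so baseline titre may predict little. Adjustment of titre is therefore only a secondary benefit.

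**The analyses are declared descriptive.** This lowers the stakes. It does not remove the point, because a descriptive analysis rests on estimates and intervals, which are what adjustment can tighten.

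**Conclusion.** The point holds as a low-cost improvement of uncertain size. The between-arm urate change comparison is unadjusted, the accompanying models name no baseline covariate, and suitable pre-randomisation values are collected.

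For a 1 SD effect the benefit over a change score ranges from none to about 25 points of power, depending on an unknown correlation and SD ratio. Where the slope is common to both arms, the worst loss in the scenarios examined was about 1–2 points; at ρ = 0, for example, power is 64% adjusted against 66% for the level alone.

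Three wider readings are not supported:

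- The comparison of patient-reported outcomes by responder status is not an arm comparison, so the point does not reach it.
- The Week 12 to Week 24 change starts from a post-randomisation value. It should stay as specified, and Week 12 should not be treated as a baseline covariate.
- Adjustment does not repair Week 24 urate lost when non-responders are discontinued and move early to Visit 17 (Sections 8.1 and 9). The calculations above assume complete data.

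**What to change.** In Section 10.4.3, name one main between-arm estimate for urate at Week 24, adjusted for the pre-randomisation value. Do the same for antibody titre. Two forms would serve:

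- ANCOVA with arm and the pre-randomisation value; or
- PROC MIXED with its fixed effects and contrasts written out, and baseline either a covariate or constrained to a common mean across arms.

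State which visit supplies the covariate: Visit 1 or pre-dose Visit 2 for urate, and Visit 1 for antibody. Visit 3 is unsuitable because it follows two weeks of randomised treatment. Keep the t-test or Wilcoxon test as a supportive analysis. Leave the Week 12 to Week 24 change and the responder-status comparison as they are.

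The cost is a few sentences of text and one degree of freedom, with no new data collection.

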5 STUDY DESIGN

5.1 OVERALL DESIGN

Hypothesis: MMF for 12 weeks can safely attenuate immunogenicity conferred by pegloticase as determined by the proportion of participants achieving and maintaining an sUA ≤ to 6 mg/dL through 12 weeks, compared to concurrent controls

Phase of trial: Phase II

Design of trial: Randomized, double-blind, placebo controlled

Single or multi-site: Multisite (UAB, University of Michigan[UM], and up to 6 to be named sites)

Number of Arms: Two arms; Intervention Arm: pegloticase + MMF (peg + MMF); Placebo Comparator Arm: pegloticase

+ placebo (peg + PBO)

Methods to minimize bias: Participants will be randomized 3:1 to either peg+MMF or to peg+PBO. Randomization allocation will be balanced by site to achieve 24 peg+MMF and 8 peg+PBO using the double-blind design

During the first 12 weeks, participants randomized to the peg+MMF arm will receive a combination of pegloticase and MMF. Patients experience reduced immunogenicity when a loading dose of anti-proliferative agent is administered *prior* to a monoclonal antibody in other disease states, ²⁷⁻³⁰ thus, for those randomized to the peg+MMF arm we will begin a MMF run-in at 500 mg/twice per day for the first week, and if tolerated titrate the dose up to 1000mg/twice per day for the second week of run-in prior to initial pegloticase infusion. MMF (or matching PBO in the other arm) will be titrated to 1000 mg/twice per day (a standard, well-tolerated dose used in other rheumatic diseases)⁶ concurrent with the first pegloticase infusion. Next, a total of up to 12 infusions of pegloticase 8 mg IV will be administered on a biweekly basis. To understand the long-term efficacy (durability) and safety of this approach, and to minimize the exposure to MMF, following the first 12 weeks of dual therapy phase, all participants will be given an additional three months of open-label pegloticase only therapy (see **Figure 1**) and will be followed.

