7.3 MEASURES TO MINIMIZE BIAS: RANDOMIZATION AND BLINDING

Participants will be randomized 3:1 to either pegloticase + MMF (Peg+MMF) or to pegloticase + placebo (peg+PBO). Randomization allocation will be balanced in time and by site to achieve 24 peg+MMF and 8 peg+PBO using a double-blind design. Treatment assignment will be determined by a random number generator and stratified by site using a central randomization system to ensure the 24/8 allocation. If any concerns arise during the randomization procedures, both the pharmacist and study coordinator will contact the Data Coordinating Center (DCC) at UAB. The UAB IDS will be responsible for assignment of randomization sequence. A drug log will be used to track the study drug from pharmacy to each randomized study participant. The centralized management of the medication will allow maintenance of a double-blind trial.

As all participants and study investigators will be blinded to treatment assignment. If there is a serious adverse event, then unblinding will be discussed and if deemed necessary to unblind the participant, then the ID of the unblinded participant, reasons for unblinding, name of the pharmacist and a list of whomever becomes unblinded will be kept in the study binder and centrally at the Data Coordinating Center and Central Pharmacy. The pharmacist will contact that participant's primary physician about the exposure. If necessary, the participant will be withdrawn from the study. NIAMS and the DSMB via KAI will be informed of any unexpected unblinding via email or at the scheduled DSMB meetings.

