9 STUDY ASSESSMENTS AND PROCEDURES

This study will be coordinated by the University of Alabama at Birmingham (UAB). All study visits and procedures will be performed at the United States, at UAB, the University of Michigan, and up to 6 to be named sites. Enrollment will be competitive between sites. Frequency of study visits and clinical evaluations can be found in **Table 1**. Following the first 12 week dual therapy phase, participants will be given an additional three months of open-label pegloticase only therapy (see **Figure 1**) and will be followed to better understand the long-term efficacy (durability) of this approach, which is essential for future studies. Specifically, we will whether assess the durability of the short course of MMF continues over the next 12 weeks in the absence of MMF.

Participants will be seen according to schedule of visits and evaluations outlined in **Table 1** and per the details that follow:

Visit 1 - Screening Visit

The screening visit will take approximately 1 hour to complete. Potential participants will be screened to determine if they satisfy all inclusion and exclusion criteria. Men and women 18 years of age or older will be invited to proceed with informed consent (IC) and enroll in the study. At the screening visit, the study objectives will be explained to potential participants. After all questions raised by a potential participant are answered, and before any protocol-specified screening procedures are initiated, they will be offered the IC for the screening evaluation. A copy of the signed and dated IC form must be provided to the participant. After IC is obtained, a participant number will be assigned. All screening procedures must be completed and eligibility criteria met prior to start of immune-modulating therapy and pegloticase infusions. Basic demographic information and reason(s) for exclusion must be completed on the specified case report form (eCRF) pages for all participants who signed an ICF, but never received pegloticase. During the screening visit, the following procedures will be performed, and information will be obtained to determine eligibility to continue in this research study:

- o Review inclusion/exclusion criteria
- o ICF
- o Date of birth
- Self-reported race/ethnicity
- Medical history that might preclude study participation
- Gout history and symptom severity
- Medication review

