10.4.2 ANALYSIS OF THE PRIMARY EFFICACY ENDPOINT(S)

MMF efficacy will be examined by the proportion of responders and tested against the control group rate using Fisher's exact test. Success rates of the efficacy primary outcome will be determined using summary statistics and 95% confidence intervals. As stated in section 10.4.1, should the success rates fall within the green area of **Figure 4** we will recommend testing in a larger study assuming safety and a demonstrated effect on Ab titers, our presumed intervening variable. We will examine failures and responders descriptively and via graphical methods.

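### Allocation is stratified by site but no planned between-arm analysis includes site; a three-level site factor would recover a little precision for continuous outcomes if sites differ materially

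*Combined protocol and SAP*

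**What the plan says.** **Design.** Section 7.3: "Treatment assignment will be determined by a random number generator and stratified by site using a central randomization system to ensure the 24/8 allocation". It adds: "Randomization allocation will be balanced in time and by site to achieve 24 peg+MMF and 8 peg+PBO using a double-blind design". Section 5.1 describes the trial as "Multisite (UAB, University of Michigan[UM], and up to 6 to be named sites", so between two and eight sites may share 32 participants, 8 of them on placebo. Section 9 adds: "Enrollment will be competitive between sites".

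**Analysis.**
- Primary endpoint (10.4.2): "MMF efficacy will be examined by the proportion of responders and tested against the control group rate using Fisher's exact test". The green zone of Figure 4 is a two-tailed Fisher p below 0.10 favouring MMF (10.4.1).
- Week 24 and week 12 to 24 responders (10.4.3): Fisher's exact test.
- Continuous secondary outcomes (10.4.3): t-tests or Wilcoxon tests.
- Antibody (10.4.3): an analysis that "compares the treatment groups using two group t-tests and regression analyses that include the time of the sampling", plus a repeated-measures PROC MIXED analysis.
- Serum urate (10.4.3): "Analyses of the sUA will be similarly assessed using PROC MIXED with random effects for participant".
- Areas under the curve (10.4.3): linear models with an offset for time under study.

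Within section 10, site is used only in 10.4.4, where demographics are summarised by group and site. No reason is given for leaving it out elsewhere.

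**The concern.** When allocation is balanced within site, differences between sites largely cancel out of the arm comparison. An analysis that ignores site still counts those differences as error. The result is not bias and not excess false positives. It is the reverse: intervals wider than they need be and a test below its nominal size.

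The antibody comparison is where this matters most. Section 10.4.1 turns to the antibody assays after a yellow or red Figure 4 result, and 10.4.2 makes a green recommendation depend on a demonstrated titre effect as well. So the comparison bears on every Figure 4 outcome, and it rests on 8 controls.

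**Working it through.** **1. The plan's own figures.**
- Section 10.2 gives 82 per group (60% vs 80%, 80% power, two-sided 5%). With pooled variance: [1.960·√(2·0.7·0.3) + 0.842·√(0.6·0.4 + 0.8·0.2)]² / 0.2² = (1.270 + 0.532)² / 0.04 ≈ 81.2, rounded up to 82. Reproduced.
- Three Figure 4 p-values also reproduce: 8/24 vs 0/8 = 0.08; 10/24 vs 1/8 = 0.21; 22/24 vs 5/8 = 0.09.
- The 73% power in 10.4.1 for a 1 SD titre difference comes with no alpha. A t-test with 24 vs 8 gives 65.9% at two-sided 0.05 and 77.3% at 0.10. The baseline below is about 66%.

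**2. How far the standard error is off.** Let ρ be the between-site share of variance, σ² the total variance and k the number of equal sites, each with exact 3:1 allocation.
- True variance of the arm difference: σ²(1−ρ)(1/24 + 1/8) = σ²(1−ρ)/6.
- Variance that the pooled t-test expects: σ²[(1−ρ) + fρ]/6, with f = (24 + 8)(1 − 1/k)/30. So f = 16/30 = 0.533 for k = 2 and 28/30 = 0.933 for k = 8.
- Ratio of planned to true standard error: √{[(1−ρ) + fρ]/(1−ρ)}.

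| ρ | 2 sites | 8 sites |
|---|---|---|
| 0.05 | √(0.9767/0.95) = 1.014 | √(0.9967/0.95) = 1.024 |
| 0.10 | √(0.9533/0.90) = 1.029 | √(0.9933/0.90) = 1.051 |
| 0.20 | √(0.9067/0.80) = 1.065 | √(0.9867/0.80) = 1.111 |

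Simulated type I error of the plain t-test at nominal 5% agrees: at ρ = 0.20 about 4.1% with two sites of 16 and 3.0% with eight sites of 4. With site in the model it is 5.2% and 5.0%.

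**3. Power with uneven sites.** Simulation with 3:1 blocks of 4 cut off at the site's size, 1 SD difference, two-sided 0.05. Site sizes and ρ are assumptions. There were 6,000 trials per setting (4,000 for the second layout), so one figure has a Monte Carlo error of about √(0.66·0.34/6000) = 0.6 points. Entries are power in % for no site term / one term per site / three levels.

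| Site sizes | ρ = 0 | ρ = 0.05 | ρ = 0.10 | ρ = 0.20 |
|---|---|---|---|---|
| 11,9,4,3,2,1,1,1 | 65.2/59.1/64.6 | 66.5/61.5/66.9 | 66.8/63.7/67.4 | 68.3/68.2/71.2 |
| 9,7,5,4,3,2,1,1 | 65.7/60.5/65.1 | 65.5/61.9/66.0 | 66.8/65.0/67.7 | 69.5/70.1/71.7 |
| 12,8,4,4,2,2 | 65.7/63.3/65.1 | not run | 68.2/69.3/70.1 | 68.9/73.2/72.2 |

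Three levels against no site term:
- ρ = 0: −0.6 in each layout.
- ρ = 0.05: +0.4 and +0.5, which is nil in practice.
- ρ = 0.10: +0.6, +0.9 and +1.9.
- ρ = 0.20: +2.9, +2.2 and +3.3.

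With exactly three sites (14, 10, 8) nothing is pooled, and the gain at ρ = 0.20 is 75.1 − 69.9 = 5.2.

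One term per site, at ρ = 0, changes power by −6.1, −5.2 and −2.4 points. Type I error of the three-level model was 4.4 to 5.4%.

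**4. Primary endpoint.** Pooled Fisher / exact site-stratified test, two-sided 0.10, 60% vs 80%, two sites of 12:4, by full enumeration:

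| Gap between sites' control rates | Type I error | Power |
|---|---|---|
| 0 points | 0.059/0.063 | 24.5/25.9% |
| 20 points | 0.053/0.065 | 22.8/23.8% |
| 40 points | 0.038/0.062 | 17.9/19.2% |

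With eight sites of 4, modest site variation (logit SD 0.5) and 60% vs 95%, Fisher has 70.7% and the stratified test 69.2%. The stratified test is not reliably better.

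**The case against.** The strongest reply is that the omission does no harm to validity. The error is conservative. Section 10.2 says that the trial is not fully powered, and 10.4.3 calls the primary and secondary analyses descriptive. With up to eight sites and 8 placebo participants, leaving out sparse strata can be defended. Material gains need a between-site share near 20%, and nothing in the documents supports that figure. Antibody samples go to one UAB laboratory and infusion prophylaxis is standardised (sections 9 and 9.3.8.1), which removes some sources of site variation. Section 10.4.3 also mentions exploratory covariate analyses without listing covariates, so site is unmentioned rather than excluded.

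Most of this stands. It limits the size of the point and rules out a blanket term for every site. It does not remove the point, because the titre comparison feeds the go decision and the three-level factor costs almost nothing even if sites are alike.

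A reader might infer that power is lost whenever sites differ. The figures do not support that: at a 5% share the gain is about half a point, and one term per site then lowers power in the uneven layouts. A reader might also infer that the primary test should be stratified. With many small sites no gain is assured.

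**Conclusion.** The omission is confirmed: site is a stratification factor, and no named between-arm test or model includes it. For continuous outcomes the planned standard errors are somewhat too large if sites differ materially, by about 3 to 11% at a 10 to 20% between-site share. The three-level factor then gains about 1 to 4 points of power for a 1 SD antibody difference (about 5 in the one layout with exactly three sites). The gain is negligible at 5% or less, and the cost is under 1 point if sites do not differ.

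This is a modest, cheap improvement in precision. It does not mean that the planned tests are biased or anti-conservative, or that the Figure 4 rule is invalid.

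The sizes rest on assumed site variance and site sizes, near-normal titres and complete data on 32 participants. The simulations cover a single continuous outcome. The mixed and area-under-the-curve models should move in the same direction but were not simulated, nor was the Wilcoxon fallback.

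**What to change.** 1. In 10.4.3, add a fixed site factor with three levels (UAB, UM, all other sites pooled) to the antibody regression, the antibody and serum urate PROC MIXED models and the area-under-the-curve linear models.
2. For continuous secondary outcomes, replace the two-group t-test with the same linear model, arm plus site.
3. State the pooling rule before unblinding. Do not fit a separate fixed term for each site when there are many small sites: that lost about 2 to 5 points in most uneven layouts tried, and about 6 in the most uneven one.
4. Keep the pooled Fisher test and Figure 4 as the basis of the primary decision. An exact test stratified by site may be reported beside it as supportive only.

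If the team prefers to leave site out, one sentence in 10.4.3 should say why.

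Cost: SAP wording and two extra degrees of freedom in each model. Site is already recorded, so no new data are needed.
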